### **5.3.2 Handling of Withdrawals and Discontinuations**

Subjects are free to withdraw from the study at any time upon request. Subject participation in the trial may be stopped at any time at the discretion of the investigator or at the request of the Sponsor or designee. At the time of withdrawal or discontinuation, the investigator will assess the best options for treatment and discuss these options with the subject.

If a subject in the study is discontinued due to any reason other than safety as detailed in [Section 4.3](#) (Safety Monitoring and Toxicity Management), another subject may be enrolled.

HIV-infected subjects who are enrolled in the IM injection study and are unable to adhere to the study schedule for IM dosing due to factors outside the study will be discontinued. Re-enrollment of HIV-infected IM Group subjects will be allowed after a Discontinuation Visit and Screening Visit are completed provided that inclusion/exclusion criteria continue to be satisfied and dosing after discontinuation is resumed according to the Trogarzo® Prescribing Information. For re-enrolling subjects, the inclusion criteria for stable a Trogarzo®-containing ARV regimen is satisfied with a loading dose of 2000mg IVI and at least one maintenance dose of 800mg IVI given according to Trogarzo® labeling prior to Day 1 enrollment.

When a subject withdraws or is discontinued from the study, the reason(s) for withdrawal or discontinuation will be recorded by the investigator. Whenever possible, all subjects who withdraw,

or are discontinued from the study prematurely will undergo all safety assessments and follow-up procedures as described for Day 99 (14 weeks) and Day 113 (16 weeks) for the Sentinel and HIV-infected IM Groups, and for Day 85 (12 weeks) and Day 99 (14 weeks) for the HIV-1 infected Core Group and the HIV-uninfected IM Group, respectively, and Day 99 for the HIV-uninfected Core Group subjects, with the exception of re-enrolled HIV-infected subjects participating in the IM study. Subjects who fail to return for final assessments will be contacted by the site personnel in an attempt to have the subjects comply with the protocol. A minimum of two documented phone calls should be made over the course of at least 2 weeks. If the site personnel receive no response, they should send a certified letter requesting that the subject contact the site regarding his or her status in the study. If the subject does not respond at this point, the date the certified letter was mailed will be considered the date of study withdrawal.

In the event of a subject death during the study, the date of death (as listed on the death certificate) will be used for the date of study discontinuation.

It is vital to obtain follow-up data on any subject withdrawn because of an AE or SAE. In such cases, the subject will be followed to satisfactory resolution or until the investigator deems the event to be chronic or the subject to be stable. In any case, every effort must be made to undertake protocol-specified safety follow-up procedures.

### **5.3.3      Sponsor or Regulatory Agency Termination of Study**

Although the Sponsor intends to complete the study, the right is reserved to discontinue the study at any time for clinical or administrative reasons, or if required by the local regulatory authority (e.g., FDA). If the Sponsor discontinues the study, FDA will be notified promptly.

## **6. Study Visits**

Subjects will complete all Screening procedures as detailed in the Schedule of Events (see [Table 1](#), [Table 2](#), [Table 3](#), and [Table 4](#)). Successful Screening results will allow the subjects to proceed to the Day 1/Baseline visit.

## 6.1 Sentinel Group

Study drug administration visits will take place once every 2 weeks beginning at Day 1/Baseline and continuing through Day 99 (14 weeks). After the study drug administration at Day 85 (12 weeks) by IV push, Sentinel Group subjects will revert to routine administration of Trogarzo® diluted in 250 mL normal saline via IVI over 15 minutes in accordance with Trogarzo® prescribing information. The scheduled visit at Day 113 (16 weeks) is for safety follow-up only, and this visit may be conducted by telephone if no clinic visit is needed for this purpose. Trogarzo® administration at Day 113/follow-up should be conducted in the routine manner as employed prior to the study, through the primary care provider.

Safety assessments, including collection of blood and urine specimens for safety laboratory testing, as well as HIV-1 viral load and archive and viral resistance samples, will be conducted every 2 weeks beginning at Day 1/Baseline and continuing through Day 99 (14 weeks). Additionally, beginning at Day 29 (4 weeks), Sentinel Group subjects will also have non-laboratory safety assessments (vital signs, AEs, recording of concomitant medications) during visits on intervening weeks between the study drug administrations that are less than 15 minutes in duration (e.g., at Day 36 [5 weeks], Day 50 [7 weeks], Day 64 [9 weeks], etc.), through Day 92 (13 weeks).

Pharmacokinetic samples will be collected after the study drug doses at Day 1/Baseline, Day 15 (2 weeks), Day 71 (10 weeks), and Day 85 (12 weeks) at the following timepoints: 1 hour, 24 hours, 72 hours, 7 days, and 14 days after study drug administration. This schedule will require additional visits solely for sample collection on Study Days 2, 4, 8, 16, 18, 22, 72, 74, 86, 88, and 92.

Pharmacokinetic samples will also be collected on Days 1, 15, 29, 43, 57, 71, 78, 85, and 99 when visits are otherwise scheduled, and extra visits are not needed on these days for collection of these samples. The 1-hour, 24-hour, and 14-day post-dose serum concentration data are required for estimation of the PK AUC.

Study participants who

1. miss 2 consecutive visits or
2. have more than one treatment visit out of window or
3. have 3 non-treatment visits over 4 weeks that are out of window

will be discontinued from the study and may be replaced. For this reason, it is important to enroll only participants who in the judgement of the investigator are likely to be compliant with the study visit and sample collection schedule.

A complete physical examination will be conducted at Screening. Targeted physical exams will be conducted at designated visit from Day 1 through Day 99 (14 weeks). Weight will be recorded at Screening and again at Day 99 (14 weeks). Immunogenicity samples will be collected at Day 1/Baseline and again at Day 99 (14 weeks). Sentinel Group subjects will be asked to return for the final study assessments indicated for the EOS and Follow-up visits at Days 99 (14 weeks) and 113 (16 weeks), respectively. Subjects who are discontinued or who withdraw from the study prematurely are also requested to complete the assessments for these 2 study visits. Refer to the Schedule of Events tables for details on procedures for each scheduled study visit and for PK sampling timepoints (for the Sentinel Group, see [Table 1](#)).

## 6.2 Core Group

Study drug administration visits will take place once every 2 weeks beginning at Day 1/Baseline and continuing through Day 85 (12 weeks). After the study drug administration at Day 71 (10 weeks), HIV-infected Core Group subjects will revert to routine administration of Trogarzo® diluted in 250 mL normal saline via IVI over 15 minutes in accordance with the Trogarzo® prescribing information. HIV-uninfected subjects will discontinue dosing after the Day 71 study drug administration. The scheduled visit at Day 99 (14 weeks) for the HIV-infected Core Group subjects is for safety follow-up only, and this visit may be conducted by telephone if no clinic visit is needed for this purpose. Trogarzo® administration at Day 99/follow-up should be conducted in the routine manner as employed prior to the study, through the primary care provider. The Day 99 EOS visit in the HIV-uninfected Core group subjects that is 28 days after the last dose of Trogarzo® must be completed in the clinic.

HIV-uninfected participants will have additional visits as per Table 2 and Table 3. HIV-uninfected subjects will receive a 2000 mg infusion over 60 minutes on Day -55 followed by 3 doses of 800 mg infusion over 15 minutes on Days -41, -27, and Day -13. Safety assessments including collection of blood and urine specimens for safety laboratory testing will be conducted every 4 weeks beginning on Day -55 and will continue through Day 1 at which time the Schedule of Events will be identical to that of the HIV-infected Core subjects.

On Day 1 HIV-1 uninfected subjects will enter the Treatment Study Phase. These HIV-uninfected subjects will receive an 800 mg dose of Trogarzo® in accordance with the prescribing information (diluted in 250 mL normal saline and administered over 15 minutes via IVI) at Day 1/Baseline and

---

again at Day 15. Every 2 weeks thereafter through Day 71 (10 weeks), subsequent doses will be administered via undiluted IV push over 30 seconds. After the Day 71 infusion (10 weeks), HIV-uninfected Core Group subjects will discontinue Trogarzo® infusion therapy.

Safety assessments, including collection of blood and urine specimens for safety laboratory testing, as well as HIV-1 viral load and archive and viral resistance samples (HIV-infected subjects only), will be conducted every 2 weeks beginning at Day 1/Baseline and continuing through Day 85 (12 weeks) for HIV-infected subjects, and through Day 99 for HIV-uninfected healthy volunteers. In addition, beginning at Day 29 (4 weeks), Core Group subjects will also have non-laboratory safety assessments (vital signs, AEs, recording of concomitant medications) conducted during visits on intervening weeks between the IV push study drug administrations (e.g., at Days 36 [5 weeks], 50 [7 weeks], 64 [9 weeks], etc.), through Day 78 (11 weeks) for HIV-infected subjects, and through Day 85 (12 weeks) for HIV-uninfected healthy volunteers.

Pharmacokinetic samples will be collected after study drug doses at Day1/Baseline, Day 15 (2 weeks), Day 43 (6 weeks), and Day 85 (12 weeks) at the following timepoints: 1 hour, 24 hours, 72 hours, 7 days, and 14 days after study drug administration. This schedule will require additional visits solely for sample collection on Study Days 2, 4, 8, 16, 18, 22, 44, 46, 72, and 74.

Pharmacokinetic samples will also be collected on Days 1, 15, 29, 43, 50, 57, 71, 78, and 85 when visit are otherwise scheduled and extra visits are not needed on these days for collection of these samples. The 1-hour, 24-hour, and 14-day post-dose serum concentration data are required for estimation of the PK AUC. In HIV-1 uninfected subjects PK samples will also be drawn on Days -55, -41, -27, and -13.

Study participants who:

1. miss 2 consecutive visits or
2. have more than one treatment visit out of window or
3. have 3 non-treatment visits over 4 weeks that are out of window

will be discontinued from the study and may be replaced. For this reason, it is important to enroll only participants who in the judgement of the investigator are likely to be compliant with the study visit and sample collection schedule.

A complete physical examination will be conducted at Screening. Targeted physical exams will be conducted at designated visits from Day 1 through Day 85 (12 weeks) for HIV-infected and through Day 99/EOS (14 weeks) for HIV-uninfected healthy volunteers. In addition, HIV-1 uninfected

---

individuals will undergo targeted physical exams on study Days -55, -41, -27, and -13. Weight will be recorded at Screening and again at Day 85 (12 weeks) for HIV-infected subjects, and at Day 99/EOS (14 weeks) for HIV-uninfected healthy volunteers. Immunogenicity samples will be collected at Day 1/Baseline and again at Day 85 (12 weeks) for HIV-infected subjects or Day 99/EOS (14 weeks) for HIV-uninfected healthy volunteers.

Core Group subjects will be asked to return for the final study assessments indicated for the EOS and Follow-up visits at Days 85 (12 weeks) for HIV-infected subjects and 99 (14 weeks) for HIV-uninfected healthy volunteers. Subjects who are discontinued or who withdraw from the study prematurely are also requested to complete the assessments for these 2 study visits. Refer to the Schedule of Events tables for details on procedures for each scheduled study visit and for PK sampling timepoints (for the Core Group, see [Table 3](#)).

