	
Laboratory samples will be collected every 2 weeks, at visits where Trogarzo® is administered. Beginning at Day 29 (4 weeks), non-laboratory safety assessments will be performed weekly through Day 99 (14 weeks) for the Sentinel Group, through Day 85 (12 weeks) for the HIV-1 infected Core Group and IM Group, and Day 99 (14 weeks) for the HIV-uninfected Core Group and IM Group.

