Review and discuss the Inclusion/Exclusion criteria	X														
Obtain a signed Informed Consent Form	X														
Record demographics, medical history (general and HIV); height	X														
Record agents in ART history at Screening, changes in ART on-study 	X	X				X				X		X			
Record results of a complete physical examination	X														
Record results of a targeted physical examination 		X				X				X	X	X		X	
Record vital sign measurements	X	X				X				X	X	X		X	
Record the subject's weight	X														
Record AEs 	X	X				X				X	X	X		X	
Record concomitant medications	X	X				X				X	X	X		X	
BLOOD and/or URINE SAMPLES TO BE COLLECTED															
Hematology and serum chemistry (see Section 7.2.1 for list)	X	X				X				X		X			

	Study Visit														
	Screening*	Day 1 Baseline	Day 2	Day 4	Day 8 (1 wk)	Day 15 (2 wks)	Day 16	Day 18	Day 22 (3 wks)	Day 29 (4 wks)	Day 36 (5 wks)	Day 43 (6 wks)	Day 44	Day 46	Day 50 (7 wks)
Visit window (days)	(-28 days)	N/A	±3 hr	±3 hr	±1	±1	±3 hr	±3 hr	±1	±1	±1	±1	±3 hr	±3 hr	±1
Urinalysis	X	X				X				X		X			
HIV-1 RNA (viral load) 	X	X				X				X		X			
4 th Generation POC HIV test 		X									X				
CD4 + cell count	X	X									X				
Serum for pregnancy test for females of childbearing potential 	X														
Urine for pregnancy test for females of childbearing potential											X				
Antiretroviral resistance sample 		X				X				X		X			
Archive serum sample		X			X					X		X			
Trogarzo® serum concentration (pre-dose if drug administered on this day) 		X	X	X	X	X	X	X	X		X	X	X	X	X
Trogarzo® serum concentration post-dose – 1 hour (±10 min)		X				X						X			
Immunogenicity of Trogarzo® (2 tubes x 3 mL each)		X													
STUDY DRUG ADMINISTRATION AND AFTER															
Administer study drug via IVI – study drug diluted in 250mL normal saline and administered IV over 15 minutes per Trogarzo® prescribing information			X				X								

	Study Visit														
	Screening*	Day 1 Baseline	Day 2	Day 4	Day 8 (1 wk)	Day 15 (2 wks)	Day 16	Day 18	Day 22 (3 wks)	Day 29 (4 wks)	Day 36 (5 wks)	Day 43 (6 wks)	Day 44	Day 46	Day 50 (7 wks)
Visit window (days)	(-28 days)	N/A	±3 hr	±3 hr	±1	±1	±3 hr	±3 hr	±1	±1	±1	±1	±3 hr	±3 hr	±1
Administer study drug via IVP – undiluted Push over 30 seconds 										X		X			

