## 8.2 Eliciting Adverse Event Information

At every study visit, subjects will be asked a standard, nondirective question, such as “How have you been feeling since your last visit?” to elicit any medically related changes in their well-being. They

will also be asked if they have been hospitalized, had any accidents, used any new medications, or changed concomitant medication regimens (both prescription and over-the-counter medications).

In addition to subject self-report, AEs will be documented from clinically significant findings resulting from abnormal laboratory test values, physical examination findings, or from other documents that are relevant to subject safety.

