## **3.4. Statistical Methods**

### **3.4.1. General Overview and Plan of Analysis**

The data collected are intended primarily for clinical review and interpretation. The analysis of study data will be primarily descriptive, with emphasis on tabular and graphical displays. Descriptive statistics will be used to guide decisions as to the clinical relevance of findings. Unless otherwise stated, p-values will be determined only if they appear to be warranted from the summary statistics.

Where applicable, summaries will be displayed in the following subject groupings:

- 1) Sentinel Group;

- 2) Core HIV-infected Group;
- Core HIV-uninfected Group and
- 3) Total.

In addition, the safety and efficacy summaries will present results for each of the dosing methods (IV push over 30 seconds, Infusion or Bolus over 10, 5, and 1 minute, and all IV infusions over 15 minutes).

For continuous data, descriptive statistics will be presented as number of subjects (n), mean, standard deviation, median, minimum, and maximum. For categorical data, the frequency and percentage of subjects in each category will be presented. Percentages will be based on non-missing data unless otherwise specified.

Data collected during this study will be assigned to the appropriate Analysis Phase, Analysis Period, and Analysis Subperiod (where applicable) in which it occurred. The assignment will be based on the visit date, or in the case of cumulative data such as AEs and concomitant procedures, based on the start date. Tables, listings, and graphs will reflect the assignments. A complete description of the phases, periods, and subperiods for the Sentinel and Core groups can be found in Appendix 1.

Data will be described and analyzed using the SAS System Version 9 (SAS Institute Inc., Cary, NC, SAS System). Individual subject data will be presented in subject data listings.

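### In the Core Group, scheduled adverse event and exam visits go from 2-weekly on infusion to weekly on push, and the IV push SAP sets periods of unequal contact and length side by side

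*Protocol*

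**What the plan says.** For the Core Group, Protocol Section 6.2 says safety assessments "will be conducted every 2 weeks beginning at Day 1/Baseline and continuing through Day 85 (12 weeks) for HIV-infected subjects". It then adds interim assessments from the first push dose: "beginning at Day 29 (4 weeks), Core Group subjects will also have non-laboratory safety assessments (vital signs, AEs, recording of concomitant medications", to be "conducted during visits on intervening weeks between the IV push study drug administrations". The Synopsis puts it this way: "Beginning at Day 29 (4 weeks), non-laboratory safety assessments will be performed weekly". Table 3 follows the same pattern for AEs, concomitant medications and the targeted exam: Days 1, 15 and 29, then weekly. One mark sits under Day 46 in the extracted table. I take it as Day 50, as the text of 6.2 has it.

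Other visits exist in the infusion weeks, but for another purpose: "This schedule will require additional visits solely for sample collection on Study Days 2, 4, 8, 16, 18, 22, 44, 46, 72, and 74". Table 3 has no AE mark on those days. Section 8.2 makes no such exception: "At every study visit, subjects will be asked a standard, nondirective question".

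In the Sentinel Group (Section 6.1, Table 1) the weekly assessments also begin after Day 29. That is when the 10-minute infusion is given; push starts at Day 71.

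Section 3.4.1 of the IV push SAP says "the safety and efficacy summaries will present results for each of the dosing methods". Mock Tables 14.3.1.1.2 and 14.3.1.1.3 place the infusion, push and follow-up periods in adjacent columns as number and percentage of the Safety Population. AEs are assigned to a period by start date. No adjustment for contacts or time is planned.

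**The concern.** Safety of the push is a primary objective, and the infusion period in the same subjects is the only reference inside the study. Anyone reading the by-period tables will compare the two columns. If subjects are asked and examined more often in one period, or followed for longer, a difference between columns may reflect how the data were collected. The two sections on AE elicitation also disagree about the infusion weeks, so sites may differ in what they record, and the tables would not show it.

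**Working it through.** The counts use visits after the first dose. I take the HIV-infected Core infusion phase as Days 1 to 29 (4 weeks) and the push phase as Days 29 to 85 (8 weeks), from the dosing days. This is an assumption, because the figures in the SAP's Appendix 1 are not shown.

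**1. Scheduled AE and exam visits, HIV-infected Core (6.2, Table 3).**
- Infusion: Days 15 and 29, so 2 / 4 = 0.5 per week.
- Push: Days 36, 43, 50, 57, 64, 71, 78 and 85, so 8 / 8 = 1.0 per week.
- Ratio 1.0 / 0.5 = 2.0. This reproduces the plan's own 2-weekly and weekly intervals.

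**2. The same subjects if 8.2 is applied at PK-only visits.**
- Infusion adds Days 2, 4, 8, 16, 18 and 22: (2 + 6) / 4 = 2.0 per week.
- Push adds Days 44, 46, 72 and 74: (8 + 4) / 8 = 1.5 per week.
- Ratio 1.5 / 2.0 = 0.75. The longest gap between contacts is 7 days in both phases.
- Section 8.2 adds no exams, so scheduled exam visits still differ 2.0-fold.

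**3. Vital signs.** Section 7.1.4 requires three sets at each dosing visit: one before and two after.
- Infusion: 2 (Day 1, after dosing) + 3 (Day 15) + 1 (Day 29, before dosing) = 6; 6 / 4 = 1.5 per week.
- Push: 2 (Day 29, after dosing) + 3 × 3 (Days 43, 57, 71) + 4 (Days 36, 50, 64, 78) + 1 (Day 85, before dosing) = 16; 16 / 8 = 2.0 per week.
- Ratio 2.0 / 1.5 = 1.33.

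**4. Core volunteers.** The SAP joins the pre-steady-state phase to the infusion period, Days -55 to 29, which is 12 weeks.
- Table 2 and Table 3: Days -41, -27, -13, 1, 15 and 29, so 6 / 12 = 0.5 per week, against 1.0 on push; ratio 2.0.
- Section 6.2 text instead gives 4-weekly safety assessments before Day 1: Days -27, 1, 15 and 29, so 4 / 12 = 0.33 per week; ratio 3.0.
- With 8.2 applied: (6 + 6) / 12 = 1.0 against 12 / 8 = 1.5 per week; ratio 1.5.

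**5. Sentinel, scheduled visits.** 15-minute infusion: 2 / 4 = 0.5 per week. Shortened infusion and bolus (Days 29 to 71): 6 / 6 = 1.0. Push (Days 71 to 99): 4 / 4 = 1.0. The step comes six weeks before push.

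**6. Period length alone.** Assume a constant hazard and equal ascertainment. If P4 is the 4-week subject incidence, then P8 = 1 − (1 − P4)² and P12 = 1 − (1 − P4)³. P4 is not in the documents, so I show a range.
- P4 = 10%: P8 = 19%, P12 = 27%.
- P4 = 30%: P8 = 51%, P12 = 66%.
- P4 = 50%: P8 = 75%, P12 = 88%.

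HIV-infected Core subjects compare P4 on infusion with P8 on push. Volunteers compare P12 with P8, which tilts the other way.

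**The case against.** The case for leaving the plan alone has weight. The question in Section 8.2 covers all the time since the last visit, so a 14-day gap is asked about in full. Section 8.3 tells subjects to contact the site whenever symptoms develop. AEs go to a period by start date, so late reporting does not move an event between columns. Acute reactions are watched for and vital signs taken in the same way after every dose. AE analysis is descriptive, and the safety objective is to evaluate push; only the PK measures are to be compared. The dose-limiting toxicity rules rest on related Grade 3 or higher events (with Grade 2 infusion reactions in Sentinel), not on mild transient ones. Watching a new route more closely is defensible.

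All of this stands, and it limits the point: the effect is on the reading of descriptive tables, and its size cannot be stated.

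Three stronger readings are tempting, and the documents do not support them.
- A reader might infer that doubled visits produce a false doubling of AEs. That needs an assumption such as events being lost unless asked about within 7 days (7 / 14 = 50% captured, against 100%). The protocol gives no such recall window, and the cumulative question and open reporting work against it.
- A reader might infer from the 0.75 ratio that the bias reverses if 8.2 is followed. With a longest gap of 7 days in both phases, that 7-day model gives full capture in both. For volunteers the ratio stays above 1 under either section.
- A reader might infer that everything doubles when push begins. Vital-sign sets rise 1.33-fold, and in Sentinel the change does not coincide with push.

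**Conclusion.** The point holds in a limited form. In the Core Group, scheduled AE, concomitant-medication and exam assessments go from 0.5 to 1.0 per week when push starts. Sections 6.2 and 8.2 disagree on whether AEs are elicited at the PK-only visits, so ascertainment on infusion is not fixed by the plan. Period length differs whichever section is followed, given the period limits assumed above. It can matter more than visit frequency: with a 30% 4-week incidence, the HIV-infected columns would read 30% and 51% with no true difference. The visit ratios are direct counts; the period-length figures rest on the constant-hazard assumption. The size of any ascertainment bias remains unknown. The repair is cheap enough that it should be made.

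**What to change.** In Tables 1 and 3 and Sections 6.1 and 6.2, record AEs and concomitant medications at the existing Day 8 and Day 22 visits. These fall 7 days after the infusions, as Days 36, 50, 64 and 78 fall 7 days after the Core push doses. Make the tables and Section 8.2 agree for all PK-only visits.

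In the IV push SAP:
- Add by-period AE rates per person-time, or per dose.
- Add a table of AEs with onset within 7 days after each dose.
- Show volunteers' Days 1 to 29 separately from the pre-steady-state phase.

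Do not use a table restricted to events first reported at dosing visits. It would drop Core push events first reported at Days 36, 50, 64 and 78, including onsets inside the 7-day window used for dose-limiting toxicity. It would also leave the length imbalance untouched.

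If Core visits are already complete, the SAP changes can still be made, with the number of AE contacts actually held reported by period.

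The cost is a few minutes at visits already held, slightly more AE data entry on infusion, and one or two supplementary tables.
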